2.5.1.5 Sensitivity analyses

The following sensitivity analysis will be performed for the primary estimand to assess the robustness of the estimation in the presence of deviations from the assumptions specified in the primary analysis. The sensitivity analysis will be implemented with the same target population, the primary variables and the summary measure as for the primary estimand, but using the different assumptions or handling of intercurrent events.

Sensitivity analysis: The change from baseline in UAS7 score up to week 12 will be imputed using zero (i.e., no clinical improvement from baseline) for the intercurrent event of “Intake of strongly confounding prohibited medication (e.g. biologics treatment at any time before Week 12, cyclosporin after Week 8 to Week 12, systemic corticosteroids after Week 8 to Week 12)” handled with composite strategy.

2.5.1.6 Supplementary analyses

Supplementary estimand

The clinical question of interest is: What is the effect of remibrutinib treatment versus placebo on the change from baseline in UAS7 score after 12 weeks treatment in adult patients with CSU who are inadequately controlled by H1-antihistamine and receiving a stable locally label approved dose of a second generation H1-antihistamine, regardless of treatment discontinuation

for any reason and regardless of intake of a different second generation H1-antihistamine as rescue medication, and as if strongly confounding prohibited medication was not taken?

The supplementary estimand is described by the following attributes:

1. **Population:** patients with inadequately controlled CSU despite treatment with second generation H1-antihistamine who have CSU duration ≥ 6 months, a UAS7 score ≥ 16 , ISS7 score ≥ 6 and HSS7 score ≥ 6 in the last 7 days prior to randomization.
2. **Endpoint:** Change in UAS7 from baseline at Week 12.
3. **Treatment of interest:** the randomized study treatment (remibrutinib 25 mg b.i.d. or placebo) regardless of treatment compliance, with background medication of local approved second generation H1-antihistamine, and a different second generation H1-antihistamine as rescue medication.
4. **Summary Measurement:** the mean difference between treatment groups.
5. **Handling of intercurrent events:**
 - Discontinuation of study treatment prior to Week 12 due to any reason: **Treatment policy strategy** (same as in [Section 2.5.1.3](#))
 - Intake of rescue medication as per protocol, or switch of background medication, or intake of other prohibited medication (except for strongly confounding prohibited medication listed below), or participants non-compliant to treatment prior to Week 12: **Treatment policy strategy** (same as in [Section 2.5.1.3](#))
 - Intake of strongly confounding prohibited medication (e.g. biologics treatment at any time before Week 12, cyclosporin after Week 8 to Week 12, systemic corticosteroids after Week 8 to Week 12): **Hypothetical strategy** will be applied irrespective of potential occurrence of other intercurrent events. Measurements after this event will be excluded from the analysis and will be imputed via a modeling approach.
 - For participants in the active treatment arms, hypothetical data will be imputed using multiple imputation under missing at random (MAR) assumptions using LOU064 data.
 - For participants in the placebo arm, hypothetical data will be imputed using multiple imputation under MAR assumptions using Placebo data.

For detailed data handling, please see [Section 2.5.1.3](#) and [Section 2.5.1.4](#).

2.5.2 Analysis supporting secondary objectives

2.5.2.1 Secondary endpoint(s)

The secondary endpoints of the scenario with UAS7 as the primary efficacy endpoint are as follows:

1. Disease activity control at Week 12, assessed as % of participants achieving UAS7 ≤ 6 .
2. Complete absence of hives and itch at Week 12, assessed as % of participants achieving UAS7 =0.

3. Improvement of severity of itch at Week 12, assessed as absolute change from baseline in ISS7 score.
4. Improvement of severity of hives at Week 12, assessed as absolute change from baseline in HSS7 score.
5. Disease activity control at Week 2, assessed as proportion of participants achieving $UAS7 \leq 6$.

For derivation of UAS7, HSS7 and ISS7 scores, please see [Section 2.5.1.1](#). The response variables (e.g., $UAS7 \leq 6$) will be derived using the corresponding weekly score.

6. No impact on participants' dermatology quality of life at Week 12, assessed as proportion of participants achieving $DLQI = 0-1$.

Seven scores will be derived from the DLQI: the score of each of the six dimensions as well as the total score of the DLQI will be calculated based on the developers' rules.

For the DLQI subscale and total score derivation, if there is only one missing score per visit, then it will be imputed to 0 and then the subscale including this item and the total score will be calculated accordingly. If there are two or more missing scores per visit, then the score will be missing.

7. Cumulative number of weeks that participants achieve $UAS7 \leq 6$ responses between baseline and Week 12.

The cumulative number of weeks achieving $UAS7 \leq 6$ response between baseline and Week 12 will be derived based on the eDiary (possible range 0-12).

8. Cumulative number of weeks that participants achieve $AAS7 = 0$ responses between baseline and Week 12.

The cumulative number of weeks achieving $AAS7 = 0$ response between baseline and Week 12 will be derived based on the AAS eDiary (possible range 0-12). The $AAS7 = 0$ response will be derived using the weekly score as described below.

Derivation of AAS7 score: A weekly AAS7 score will be derived by adding up the daily scores (possible ranges 0 to 15) of the 7 days preceding the visit, and ranges from 0 to 105 (please refer to the assessment window in [Section 2.1.1.5](#)). If one or more of the daily scores are missing, the following principles will be applied to handle the missing data: If a participant has at least 4 non-missing daily scores within the 7 days, ASS7 will be calculated as the sum of the available scores of that week, divided by the number of non-missing days, multiplied by 7. If there are less than 4 non-missing daily scores within the 7 days, ASS7 will be considered as missing for that week.

Secondary estimand

For each secondary endpoint, the following secondary estimand will be considered:

The secondary clinical question of interest is: What is the effect of remibrutinib treatment versus placebo on secondary endpoints after 12 weeks treatment in adult participants with CSU who are inadequately controlled by H1-antihistamine and receiving a stable locally label approved dose of a second generation H1-antihistamine, regardless of treatment discontinuation for any reason and regardless of intake of a different second generation H1-antihistamine as rescue medication and considering strongly confounding prohibited medication as an unfavourable outcome?

The secondary estimand is described by the following attributes:

1. **Population:** patients with inadequately controlled CSU despite treatment with second generation H1-antihistamine who have CSU duration \geq 6 months, a UAS7 score \geq 16, ISS7 score \geq 6 and HSS7 score \geq 6 in the last 7 days prior to randomization.
2. **Endpoint:** see below
3. **Treatment of interest:** the randomized study treatment (remibrutinib 25 mg b.i.d. or placebo) regardless of treatment compliance, with background medication of locally label approved dose second generation H1-antihistamine, and a different second generation H1-antihistamine as rescue medication.
4. **Summary Measurement:** see below
5. **Handling of intercurrent events:** the intercurrent events are the same for the primary endpoint as described in [Section 2.5.1.3](#). For the handling of intercurrent events, please see below.

Table 2-12 Estimand attributes for secondary endpoints

Endpoint	Summary measurement	Handling of intercurrent event
UAS7 \leq 6 at Week 12	Odds ratio between treatment groups	A treatment policy strategy: RDO data or data collected after the IE will be used. In case of missing values of RDO data, derivation based on the multiply imputed UAS7 described in Section 2.5.1.3 will be applied.
		A composite strategy: UAS7 response after the intercurrent event will be excluded and UAS7 \leq 6 will be derived from imputed UAS7 score using the worst value (i.e., 42).
UAS7 = 0 at Week 12	Odds ratio between treatment groups	Same as UAS7 \leq 6 at Week 12.
ISS7 score change from baseline to Week 12	Mean difference between treatment groups	Same as the primary estimand, see Section 2.5.1.3
HSS7 score change from baseline to Week 12	Mean difference between treatment groups	Same as the primary estimand, see Section 2.5.1.3
UAS7 \leq 6 at Week 2	Odds ratio between treatment groups	Same as UAS7 \leq 6 at Week 12.

Endpoint	Summary measurement	Handing of intercurrent event
		Note: As this endpoint is for the score at W2, some intercurrent events, e.g. intake of strongly confounding prohibited medication, will not be considered.
DLQI 0/1 at Week 12	Odds ratio between treatment groups	Same as UAS7 \leq 6 at Week 12. In case of missing values of RDO data, derivation based on the multiply imputed DLQI score with same approach as UAS7 will be applied.
Cumulative number of weeks with an UAS7 \leq 6 response between baseline and Week 12	Ratio of response rate between treatment groups	Same as UAS7 \leq 6 at Week 12. Derivation based on the multiply imputed UAS7 described in Section 2.5.1.3 will be applied.
Cumulative number of weeks with an AAS7=0 response between baseline and Week 12	Ratio of response rate between treatment groups	Same as UAS7 \leq 6 at Week 12. Derivation based on the multiply imputed AAS7 with same approach as UAS7 will be applied.

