- No impact on participants' dermatology quality of life at Week 12, assessed as proportion of participants achieving DLQI = 0-1.

An overall score will be calculated according to the scoring manual. The proportion of participants with overall DLQI scores ≤ 1 at Week 12 will be analyzed using a logistic regression model which includes treatment group, region, prior exposure to anti-IgE biologics and baseline DLQI score.

- Cumulative number of weeks that participants achieve $UAS7 \leq 6$ responses between baseline and Week 12.

The cumulative number of weeks achieving $UAS7 \leq 6$ response between baseline and Week 12 will be derived based on the eDiary. The cumulative number of weeks achieving $UAS7 \leq 6$ response between baseline and Week 12 will be modelled using a negative binomial regression model with log link, using treatment group, region, and prior exposure to anti-IgE biologics. The number of weeks stay on the trial will be used as an offset.

- Cumulative number of weeks that participants achieve $AAS7 = 0$ responses between baseline and Week 12.

The cumulative number of weeks achieving $AAS7 = 0$ response between baseline and Week 12 will be derived based on the AAS eDiary and UPDD diary. A weekly AAS7 score will be derived by adding up the daily scores of the 7 days preceding the visit, and ranges from 0 to 105. If the AAS7 assessment is missing, it will be considered as a non-response for the cumulative number of weeks that participants achieve $AAS7 = 0$ response calculation.

The cumulative number of weeks achieving $AAS7 = 0$ response between baseline and Week 12 will be modelled using a negative binomial regression model with log link, using treatment group, region, prior exposure to anti-IgE biologics and baseline $AAS7 = 0$ status.

Statistical model, hypothesis, and method of analysis for scenario with UAS7 as the primary efficacy endpoint

Testing strategy

The following null hypotheses (H_0) will be tested against the respective alternative hypotheses (H_A) in a closed testing procedure (Bretz et al 2009), thus controlling the family-wise type I error which is set to 0.025 (one-sided):

Primary:

UAS7 score change from baseline at Week 12

$$H_{01}: \mu_{\text{remibrutinib}} \geq \mu_{\text{Placebo}} \text{ versus } H_{A1}: \mu_{\text{remibrutinib}} < \mu_{\text{Placebo}}$$

where μ is the mean change from baseline in UAS7 at Week 12,

Secondaries:

- **UAS7 ≤ 6 at Week 12**

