2.5.2.4 Handling of missing values

See [Section 2.5.1.4](#) for missing data of continuous variables. Missing data of response variables will be derived using the multiply imputed data for corresponding continuous variables.

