5.4.2.3 Negative binomial regression

Count variable including the cumulative number of weeks achieving AAS7= 0 response between baseline and Week 12 or the cumulative number of weeks achieving UAS7≤6 response will be modelled using a negative binomial regression model with log link, using treatment group, randomization strata factors (i.e. geographic region and prior exposure to anti-IgE biologics, and baseline AAS7=0 status (for AAS7 = 0 response only). The patient's time in the treatment period up to Week 12 (natural log of proportion of time in treatment period, i.e., natural log of [number of weeks with the response variable in treatment period/12 weeks]) is used as an offset variable. The patient's time in the treatment period up to Week 24 (natural log of proportion of time in treatment period, i.e., natural log of [number of weeks with the response variable in treatment period/24 weeks]) is used as an offset variable.

If the AAS7 = 0 (respectively UAS7≤6) assessment is missing, it will be considered as a non-response for the cumulative number of weeks that participants achieve AAS7= 0 response calculation (respectively UAS7≤6).

The negative binomial model accounts for any over dispersion that may result from assuming a Poisson distribution by allowing a different Poisson rate for each patient and assuming that these rates as a set are distributed across participants according to a gamma distribution.

The SAS procedure PROC GENMOD will be used for this analysis with the following code:

```
proc genmod data=...;  
  by impnb;  
  class trt01p antige region/ param = glm;  
  model count = baseline trt01p antige region/ DIST= NEGBIN LINK= LOG  
  offset=offset;  
  lsmeans trt01p / cl exp diff ilink e OM;  
  estimate "LOU064 v.s pbo" trt01p 1 -1;
```

```
ods output Estimates=estimates LSMeans=lsmeans;
run;
```

where baseline = baseline AAS7=0 status (for AAS7 = 0 response only).

The SAS procedure PROC MIANALYZE will be used to combine the results. The risk ratio and the 95% confidence interval for the risk ratio will be generated using an exponential transformation of the model estimates.

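### The SAP handles missing AAS7 weeks in two incompatible ways, and under the imputation route a week with recorded angioedema can count as angioedema-free

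*SAP*

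**What the plan says.** **Weekly score.** SAP 2.5.2.1: "A weekly AAS7 score will be derived by adding up the daily scores (possible ranges 0 to 15) of the 7 days preceding the visit". With at least four scored days, "ASS7 will be calculated as the sum of the available scores of that week, divided by the number of non-missing days, multiplied by 7". With fewer, "If there are less than 4 non-missing daily scores within the 7 days, ASS7 will be considered as missing for that week". No sentence makes a week a non-response because angioedema was recorded on one of its days.

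**Missing weeks, route A (imputation).** Table 2-12, for the AAS7 = 0 count: "Derivation based on the multiply imputed AAS7 with same approach as UAS7 will be applied". SAP 2.5.2.4 gives the general rule: "Missing data of response variables will be derived using the multiply imputed data for corresponding continuous variables". SAP 5.4.3 specifies a multivariate Normal model on weekly scores, with 100 imputations and out-of-range draws moved to the nearest limit, so a negative draw becomes 0.

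**Missing weeks, route B (non-response).** SAP 5.4.2.3: "If the AAS7 = 0 (respectively UAS7≤6) assessment is missing, it will be considered as a non-response". Protocol 12.5.1 has the same rule for AAS7.

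**Data source.** Protocol 12.5.1 says the count "will be derived based on the AAS eDiary and UPDD diary". Item 8 of SAP 2.5.2.1 names only the AAS eDiary. SAP section 4 declares no changes to the protocol's analyses.

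**The concern.** The endpoint counts weeks without angioedema. One recorded angioedema day therefore settles the week, however many other days are blank. The four-day minimum suits an average severity score, where a few days may represent the week poorly. It does not suit a yes/no question that a single day can answer.

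Under route A that answer is lost. The week goes to missing, and the imputation model works on weekly scores, treatment, baseline, strata and week, so it never sees the daily entries. Some of the 100 completed data sets may then count the week as free of angioedema. Under route B the same week counts against response. The SAP contains both instructions and does not say which takes precedence, for a hypothesis tested under family-wise error control (H09 with UAS7 as primary, H08 with ISS7/HSS7 as co-primaries).

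**Working it through.** **1. The SAP's own range.** The AAS has five items (protocol 16.4), each scored up to 3 (protocol 8.3.1.2). 5 × 3 = 15 per day and 15 × 7 = 105 per week, as the SAP states. The documents give no power or event rate for this endpoint.

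**2. The weekly rule applied to every possible week.** Give each day one of four states: scored 0; scored positive (taken as 1, the smallest value); UPDD yes with the AAS items not scored; no entry. That gives 4⁷ = 16,384 patterns.

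| Angioedema recorded in the week | Scored days | Patterns | Result |
|---|---|---|---|
| At least one positive scored day | 4 or more | 7,813 | AAS7 > 0 in all |
| At least one positive scored day | fewer than 4 | 6,384 | missing in all |
| Only an unscored yes | 4 or more | 315 | AAS7 = 0 in all |
| Only an unscored yes | fewer than 4 | 1,744 | missing in all |

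Check: 7,813 + 6,384 = 4⁷ − 3⁷ = 14,197, and 315 + 1,744 = 3⁷ − 2⁷ = 2,059. The smallest prorated value with a positive scored day is 1/7 × 7 = 1.0. These counts show what the rule permits, not how often it happens.

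**3. The 6,384 missing patterns.** Under route B every one is a non-response and none becomes AAS7 = 0. Under route A the week is counted as AAS7 = 0 whenever the draw is at or below 0, with probability Φ(−mean/SD) for that week's conditional mean and SD. The documents give neither, so these values are assumed:

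| Assumed mean | SD 5 | SD 10 | SD 15 | SD 20 |
|---|---|---|---|---|
| 5 | 16% | 31% | 37% | 40% |
| 10 | 2% | 16% | 25% | 31% |
| 20 | <0.1% | 2% | 9% | 16% |

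**4. Scale, for illustration only.** Assume 5% of weeks have one to three scored days and 20% of those include a positive day. At the top of the grid, 0.05 × 0.20 × 0.40 = 0.004 of weeks, or 0.004 × 12 = 0.048 of a week per participant. At the bottom it is below 0.05 × 0.20 × 0.001 × 12 = 0.00012. The result scales in proportion to each assumed input.

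**5. Can the two routes be reconciled?** The program in SAP 5.4.2.3 runs by imputation and pools with PROC MIANALYZE. If imputation comes first, no week is left missing for the non-response sentence to act on. If the non-response sentence comes first, no missing week is left for the imputed score to decide. One instruction is always idle, and the SAP does not say which.

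**The case against.** The strongest reply is that the protocol and SAP 5.4.2.3 already count a missing week as a non-response, so no week with recorded angioedema can become a success. On that reading the misclassification disappears, and this stands. It does not clear the plan. Table 2-12 and 2.5.2.4 say the opposite, the model code is built for imputed data, and the SAP's change history records a change to the imputation method for missing response variables at amendment 2, which suggests imputation is intended.

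Three stronger readings are tempting, and the documents support none of them.

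- **That proration hides angioedema days.** It never turns a positive scored day into 0. It could only pass over a day answered yes in the UPDD but left unscored in the AAS. The documents do not say whether the eDiary allows that, or how a partly completed AAS day is scored.
- **That the SAP abandoned the UPDD.** The UPDD angioedema question opens the AAS, and a no sets that day's score to 0 (protocol 8.3.1.2), so every AAS day already uses the UPDD answer. The difference in source may be one of wording, and needs only confirmation.
- **That the treatment ratio is pulled toward 1.** An arm with more angioedema may have more affected weeks, but its higher imputed scores would fall at or below 0 less often. These forces oppose each other, and the documents cannot settle the net direction.

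**Conclusion.** The concern holds in limited form. The contradiction between imputation and non-response for missing AAS7 weeks is plain from the text. If imputation governs, a week with one to three scored days and a recorded positive day can be counted as angioedema-free. If non-response governs, it cannot.

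The effect is expected to be small, but that is a judgement: the documents give no rate of diary missingness and no AAS7 distribution, so neither size nor direction can be calculated. The percentages and the 0.048-week figure rest wholly on assumed inputs. AAS7 = 0 is the last hypothesis in both hierarchies, so no other test depends on it. This is a cheap clarification and no threat to the trial's main conclusions.

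**What to change.** 1. Add to SAP 2.5.2.1, before any imputation: a week with at least one daily AAS score above 0, or at least one yes to UPDD question 6a, is a non-response for AAS7 = 0 whatever the number of scored days. This also closes the possible gap from unscored yes days.
2. Keep one rule for the remaining missing weeks. Either retain the protocol's non-response rule and amend Table 2-12 and 2.5.2.4 for this endpoint, or retain multiple imputation, delete the non-response sentence for AAS7 in 5.4.2.3, and declare the change in section 4. That sentence also covers the UAS7 ≤ 6 count, so both should be settled in the same edit.
3. Confirm in section 4 that the UPDD remains a source for the endpoint, and correct ASS7 to AAS7.

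The cost is a few sentences and one derived flag from data already in the eDiary. Formal testing is confined to the primary analysis (SAP 2.13), and the latest amendment is dated before the final analysis. If the test has already been run, the flagged derivation should be reported beside it as a sensitivity analysis, stating which missing-week rule was used.

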2.5.1.3 Handling of intercurrent events

Participants who discontinue from study treatment early due to any reason will be encouraged to stay in the study following the procedures. Every effort will be made to continue to follow participants who discontinued from study treatment up to Week 12. These are considered as Retrieved drop out (RDO) participants.

The analysis will account for different intercurrent events as explained in the following:

1. Discontinuation of study treatment prior to Week 12 due to any reason:

A treatment policy strategy will be applied and these intercurrent events will be ignored. Data collection will be maintained and available measurements post-treatment discontinuation will be used as if they had been obtained under the treatment assigned at randomization. i.e, RDO data collected after study treatment discontinuation will be used for analysis. In case of missing values, a multiple imputation approach will be applied (see [Section 2.5.1.4](#) for details).

2. Intake of rescue medication as per protocol, or switch of background medication, or intake of other prohibited medication (except for strongly confounding prohibited medication listed below), or participants non-compliant (dose interruption) to treatment prior to Week 12:

A treatment policy strategy will be applied in the same way as described above. Data collected after these events will be used for analysis.

3. Intake of strongly confounding prohibited medication:

- Biologics treatment at any time before Week 12 (as identified by PD M-COMD03)
- Cyclosporin after Week 8 to Week 12 (as identified by PD M-COMD04)
- Systemic corticosteroids after Week 8 to Week 12 (as identified by PD M-COMD04)

A composite strategy will be applied. Measurements after this event will be excluded from the analysis and will be imputed using the worst value of the endpoint (i.e., 42 for UAS7).

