$H_{09}: \mu_{\text{remibrutinib}} \leq \mu_{\text{Placebo}}$ versus $H_{A9}: \mu_{\text{remibrutinib}} > \mu_{\text{Placebo}}$

where μ is the mean cumulative number of weeks that participants achieve AAS7=0 response between baseline and Week 12,

A graphical representation of the testing strategy is presented in [Figure 2-1](#)

Figure 2-1 Testing strategy with UAS7 as the primary endpoint

The value inside the circle represents the significance level. The arrow and value inside the square represent the "alpha-propagation".

The first hypothesis is tested with full level alpha (0.025 one-sided). If significant, the second hypothesis is tested with full-level alpha; otherwise, the testing procedure stops. The testing is strictly hierarchical, so that null hypotheses can be tested along the pre-defined order at the level assigned until a null hypothesis cannot be rejected, at which point the testing stops. Furthermore, the testing strategy reflects the separation of primary and secondary endpoints, so that hypotheses related to secondary endpoints will only be tested if the null hypothesis related to the primary endpoint is rejected.

Statistical model and method of analysis

1. UAS7 \leq 6 at Week 12

The proportion of participants with $UAS7 \leq 6$ at Week 12 will be analyzed using a logistic regression model including treatment group, region, prior exposure to anti-IgE biologics and baseline UAS7 score as covariate.

2. UAS7 = 0 at Week 12

The proportion of participants with $UAS7 = 0$ at Week 12 will be analyzed using a logistic regression model including treatment group, region, prior exposure to anti-IgE biologics and baseline UAS7 score as covariate.

3. ISS7 score change from baseline at Week 12

The absolute change from baseline in ISS7 score at Week 12 will be analyzed using MMRM modeling including treatment group, baseline ISS7 score, randomization strata variables, week and both interaction of treatment by week and interaction of baseline ISS7 score by week as fixed effects.

4. HSS7 score change from baseline at Week 12

The absolute change from baseline in HSS7 score at Week 12 will be analyzed using MMRM modeling including treatment group, baseline HSS7 score, randomization strata variables, week and both interaction of treatment by week and interaction of baseline HSS7 score by week as fixed effects.

5. UAS7 \leq 6 at Week 2

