3.1 Primary endpoint(s)

In order to fulfill registration and ICH E1 requirements on the number of participants treated for 6 months and 12 months in the development program, a sample size of 300 participants in the active arm and 150 in the placebo arm is targeted. Hence, the total sample size is 450 randomized participants.

From an efficacy point of view, the sample size justification is based on UAS7 change from baseline (for scenario with one primary endpoint), ISS7 and HSS7 change from baseline (for scenario with co-primary endpoints) and achievement of $UAS7 \leq 6$ and $UAS7 = 0$ at Week 12. To avoid assigning an unnecessary large number of participants to placebo, participants will be randomized in a 2:1 ratio to remibrutinib 25 mg b.i.d. and placebo arms, respectively.

All calculations were performed with nQuery Advisor 8.4.1.0 and Ri386 4.0.2 softwares.

For scenario with UAS7 as the primary efficacy endpoint

UAS7 change from baseline at Week 12

Approximately 10% drop-out is expected at week 12, thus with 270 participants in the active arm and 135 participants in the placebo arm, this gives a nominal power of more than >99% to detect a difference between remibrutinib and placebo if the mean change of UAS7 from baseline to Week 12 is at least 10 in favor of remibrutinib, with common standard deviation of approximately 12 (based on the primary endpoint analysis of Phase 2b study (CLOU064A2201)), based on a t-test, assuming type I error 0.025 (one-sided).

For scenario with ISS7/HSS7 as the co-primary efficacy endpoints

ISS7 change from baseline at Week 12

Approximately 10% drop-out is expected at week 12, thus with 270 participants in the active arm and 135 participants in the placebo arm, this gives a nominal power of more than >99% to detect a difference between remibrutinib and placebo if the mean change of ISS7 from baseline to Week 12 is at least 4 in favor of remibrutinib, with common standard deviation of approximately 6 (based on the primary endpoint analysis of Phase 2b study (CLOU064A2201)), based on a t-test, assuming type I error 0.025 (one-sided).

HSS7 change from baseline at Week 12

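### The Table 2-12 note for UAS7≤6 at Week 2 drops biologic use against the SAP's own rule, and the Week 8 cut-off for cyclosporin and corticosteroids fits the two cumulative-weeks endpoints poorly

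*SAP*

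**What the plan says.** SAP 2.5.2.1 sets one estimand for every secondary endpoint. Its clinical question ends by "considering strongly confounding prohibited medication as an unfavourable outcome", and it takes over the primary endpoint's list of intercurrent events from SAP 2.5.1.3.

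That list has three triggers for the composite strategy. The first is "Biologics treatment at any time before Week 12 (as identified by PD M-COMD03"). The third is "Systemic corticosteroids after Week 8 to Week 12 (as identified by PD M-COMD04"). Cyclosporin, the second, has the same Week 8 to Week 12 window. Other prohibited medication is handled by treatment policy, so observed scores are used. SAP 2.5.1.4 (Step 3) then gives the worst value to every visit following a composite event, not to Week 12 alone.

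Table 2-12 refers the Week 2 endpoint to the Week 12 handling and adds a note: because the score is at Week 2, "some intercurrent events, e.g. intake of strongly confounding prohibited medication, will not be considered". Both cumulative-weeks endpoints also follow the Week 12 handling, through the imputed UAS7 or AAS7 series.

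Protocol 2.2 has no Week 2 exception, and SAP Section 4 declares no change from the protocol's analyses. Sensitivity analyses for secondary endpoints are marked not applicable in both scenarios (SAP 2.5.2.5 and 2.6.2.5).

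**The concern.** The Week 2 cell gives two instructions that cannot both be programmed. The note's rationale works for cyclosporin and corticosteroids, whose window opens after Week 8. It does not work for biologics, whose window covers Weeks 1-2.

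The cumulative endpoints have a different problem. A cut-off four weeks before a Week 12 score is understandable for that score, but these endpoints add up responses over Weeks 1-12. A participant who takes a corticosteroid just before the cut-off keeps every observed week. One who takes it just after loses every later week.

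At stake are the meaning and reproducibility of three hypotheses in a strict one-sided 0.025 hierarchy: H06, H08 and H09 in the UAS7 scenario (H05, H07 and H08 in the co-primary scenario). No planned analysis would show how much the handling matters.

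**Working it through.** **1. The plan's nearest figure.** The documents give no planning figure for Week 2 or for cumulative weeks. The closest is UAS7≤6 at Week 12: 0.53 v 0.15, 270 v 135 participants (300 × 0.9 and 150 × 0.9), one-sided 0.025, continuity-corrected χ² test, stated power above 99% (SAP 3.2).

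- Corrected difference: 0.38 − ½(1/270 + 1/135) = 0.3744.
- Pooled rate: (270 × 0.53 + 135 × 0.15)/405 = 0.4033.
- Standard error under the null: √[0.4033 × 0.5967 × (1/270 + 1/135)] = 0.0517.
- Standard error under the alternative: √(0.53 × 0.47/270 + 0.15 × 0.85/135) = 0.0432.
- Power: Φ[(0.3744 − 1.96 × 0.0517)/0.0432] = Φ(6.3), above 99.99%.

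The stated figure is reproduced. Nothing below changes it.

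**2. What the rules do, by drug and time of use.**

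| Use | UAS7 in the repeated-measures model | Week 2 response test | Cumulative-weeks endpoints |
|---|---|---|---|
| Biologic in Week 1 | Later visits set to 42 | Observed score can stand, under the note | Later weeks are non-response |
| Cyclosporin or systemic corticosteroid, Weeks 1-8 | Observed (treatment policy) | Observed | Observed, so symptom-free weeks count as response |
| Cyclosporin or systemic corticosteroid, after Week 8 | Later visits set to 42 | Not applicable, use is later | Later weeks are non-response |

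Only the first row is inconsistent across analyses: the same participant in the same week has a score of 42 in one analysis and may be a responder in another.

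**3. Size at Week 2.** If a share u of an arm used a biologic by Week 2 and was counted as a responder, deleting the note lowers that arm's rate by u. The documents give neither u nor Week 2 rates. As an illustration I use the Phase 2b Week 4 rates in Protocol 4.2 (0.558 v 0.048; difference 0.510, odds ratio 25.0):

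- u = 1% in both arms: 0.548 − 0.038 = 0.510; odds ratio 30.7.
- u = 1% active, 3% placebo: 0.548 − 0.018 = 0.530.
- u = 5% active only: 0.508 − 0.048 = 0.460.

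Power at 300 v 150 stays above 99% in all three. It falls visibly only with a small effect and one-sided use: an assumed 0.20 v 0.05 has 99.5%, and 88.1% after removing 5% from the active arm alone (0.15 v 0.05).

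**4. Size in the cumulative endpoints.** A participant who uses cyclosporin or a corticosteroid at the start of Week 1 can keep at most 12 response weeks. The change in an arm's mean is therefore at most 12 × u: 0.12 weeks at 1%, 0.24 at 2%, 0.60 at 5%. Biologic users contribute nothing here, because their later weeks are already non-response. The documents give no mean number of response weeks, so I do not convert this to a ratio of rates.

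**The case against.** The strongest reply has four parts.

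- **The note is mostly a matter of logic.** Two of the three triggers cannot occur by Week 2, and SAP 2.5.2.1 leaves the handling to Table 2-12. This stands for cyclosporin and corticosteroids. It does not stand for biologics: the table may say how an event is handled, but the note removes one that the estimand's list and question keep.
- **Early cyclosporin and corticosteroid use is handled as the estimand says.** The Week 8 cut-off is part of the attribute in Protocol 2.1 and 2.2 and in SAP 1.2. This stands. A reader might infer that the cumulative analyses contradict their estimand. They do not; the window fits the endpoint badly, which is a weaker point.
- **The composite rule is not confined to Week 12.** A reader might infer that biologic use can count as response in the cumulative endpoints. It cannot after the event, since all later visits take the worst value. Use of the other two drugs after Week 8 is covered as well.
- **Such use should be rare.** Protocol 6.2.3 prohibits biologics from four months before randomization, and Protocol 6.2.4 prohibits corticosteroids for CSU before Week 12. This is a fair reason to expect a small effect, but the composite strategy exists for breaches of exactly these rules.

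**Conclusion.** The Week 2 contradiction is established from the text and concerns biologic use in Weeks 1-2 in one hypothesis. The cumulative-weeks point is a mismatch between a window set for Week 12 and a count over Weeks 1-12. It is bounded by 12 times the user share in an arm's mean: 0.12-0.60 weeks if 1-5% use these drugs in Weeks 1-8. Those shares are assumptions.

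The direction is also unknown. It may be tempting to conclude that the plan favours remibrutinib. The documents do not support this: if use is more common on placebo, counting it as response raises the placebo rate and makes the comparison conservative. Nor is there ground for saying that three hypotheses contradict their estimand; only the Week 2 one does. The primary analysis and every stated power figure are unchanged. The point is worth acting on because the tests sit in the confirmatory hierarchy and the repair is cheap, not because the numerical effect is likely to be large.

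**What to change.** 1. Delete the Week 2 note in Table 2-12, so that biologic use before Week 2 follows the composite strategy of SAP 2.5.1.3 and 2.5.1.4.
2. For the two cumulative-weeks endpoints, replace the not-applicable entries in SAP 2.5.2.5 and 2.6.2.5 with a sensitivity analysis that counts weeks after cyclosporin or systemic corticosteroid use in Weeks 1-8 as non-response. Keep the main analysis as written: a different window there would redefine an estimand fixed in Protocol 2.2.
3. Report the number of users of each drug class by arm and week.

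SAP 2.13 confines formal testing to the primary analysis. If that testing was done with the note in force, keep its result and show the aligned Week 2 analysis as a labelled sensitivity analysis.

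The cost is a little programming from medication data already collected (Protocol 6.2.1), and slightly lower response counts.
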